8.3. Deaths and Serious Adverse Events

All deaths will be summarised based on the number and percentage of subjects. This summary will classify subjects by time of death relative to the last dose of medication (>30 days or ≤30 days) and primary cause of death (disease under study, SAE possibly related to study treatment, or other). A supportive listing will be generated to provide subject-specific details on subjects who died.

All SAEs will be tabulated based on the number and percentage of subjects who experienced the event. Separate summaries will also be provided for study treatment-related SAEs. The summary tables will be displayed in descending order by PT. The summary of all SAEs will also be created by SOC and PT. In addition, a summary of cumulative incidence of SAE by number of doses received at first occurrence will be provided.

A study treatment-related SAE is defined as an SAE for which the investigator classifies the relationship to study treatment as “Yes”. A worst-case scenario approach will be taken to handle missing data, i.e. the summary table will include events with the relationship to study treatment as ‘Yes’ or missing.

SAEs are included in the listing of all adverse events. Separate supportive listings with subject-level details will be generated for

- Fatal SAEs
- Non-Fatal SAEs.

8.4. Adverse Events Leading to Discontinuation and Dose Modification

The following categories of AEs will be summarized separately by PT and separate supportive listings will be generated with subject level details for those subjects:

- AEs Leading to Permanent Discontinuation of Study Treatment
- AEs Leading to Dose Interruptions or Delays
- AEs Leadings to Dose Reductions

8.5. Ocular findings from ophthalmic exam

As outlined in study protocol (Version: GSK Document Number [TMF-13990464](#)) Schedule of Activities (Table 1 of Section 1.2), ophthalmic exams are scheduled at

screening, during the study, and follow-up period for subjects in both general study and ocular sub-study. The ocular findings from ophthalmic exams will be analysed as described below.

1. For general study from baseline to last follow-up, the following analysis will be performed:
 - a. Best corrected visual acuity (BCVA): BCVA (logMAR score) at baseline, EOT visit, and last follow-up visit as well as worst and most frequent category (definite worsen, possible worsen, and no change/improved) of change from baseline will be summarized by eye (R/L) and subject (worse eye and better eye). Number (%) of subjects with a decline in BCVA to 'light perception' (LP) or 'no light perception' (NLP) due to corneal finding anytime post-baseline will also be provided.
 - b. Intraocular Pressure (IOP): summary table of 1) Number (%) of subjects with IOP \geq 22mm Hg anytime post-baseline; 2) Number (%) of subjects who start treatment for IOP after 1st dose of study drug.
 - c. Pupillary Exam: shift table (Normal to Abnormal) from baseline to worst post-baseline by subject (worse eye)
 - d. Extraocular Muscle Movement: shift table (Full Intact: Yes to No) from baseline to worst post-baseline by eye (R/L) and subject (worse eye)
 - e. External Exam: shift table (Ptosis: No to Yes) from baseline to worst post-baseline by eye (R/L) and subject (worse eye)
 - f. Lids/Lashes/Lacrimal System: shift table (Blepharitis/MGD: No to Yes) from baseline to worst post-baseline by eye (R/L) and subject (worse eye)
 - g. Conjunctival Exam:
 - i. shift table (Chemosis: Absent to Present; Bulbar Conjunctiva White and Quiet: Yes to No; Palpebral Conjunctiva within normal limits: Yes to No) from baseline to worst post-baseline by eye (R/L) and subject (worse eye)
 - h. Sclera: shift table (Scleritis: No to Yes) from baseline to worst post-baseline by eye (R/L) and subject (both eyes in same ocular exam)
 - i. Corneal Exam:
 - i. Corneal epithelium findings:
 1. Shift table from baseline to worst post-baseline by eye (R/L) and subject (worse eye) for Corneal epithelium (Normal to Abnormal), Corneal ulcer (No to Yes), Microcystic edema (No to Yes), Microcystic without edema (Yes/No), Subepithelial haze (No to Yes), Corneal neovascularization (No to Yes), Stroma (Normal to Abnormal), Active opacity (No to Yes), and Active edema (No to Yes).
 2. For punctate keratopathy, summary table of worst grade and most frequent grade across ocular exams by eye (R/L) and subject (worse eye)
 - ii. Corneal endothelium findings:

1. Shift table from baseline to worst post-baseline by eye (R/L) and subject (worse eye) for Corneal endothelium (Normal to Abnormal)
 2. Summary table by eye (R/L) and subject (either eye) for presence of Descemet's folds and Endothelial lesion at any post-baseline ocular exam.
- j. Pachymetry: Summary table of number (%) of $\geq 5\%$ increase from baseline at worst post-baseline by eye (R/L) and subject (either eye)
- k. Schirmer's Test/ Tear Break-up Time:
- i. Summary table of change from baseline to worst post-baseline by eye (R/L).
 - ii. Shift table from baseline to worst post-baseline by eye (R/L). The categories for Schirmer's Test are ≤ 5 mm, > 5 and ≤ 10 mm, and > 10 mm; the categories for Tear Break-up Time are: ≤ 5 sec, > 5 and ≤ 10 sec, and > 10 sec.
- l. Slit Lamp Exam:
- i. Shift table from baseline to worst post-baseline by eye (R/L) and subject (worse eye) for Anterior Chamber: Deep/Quite (Yes to No); Iris: Flat, round and reactive (Yes to No); and Lens: Clear (Yes to No).
 - ii. Summary tables of presence of iris findings ('Transillumination defect', 'Nodules', or 'Neovascularization') at any post-baseline ocular exam.
 - iii. Shift table from baseline to worst post-baseline by eye (R/L) and subject (worse eye) for Pseudophakia (No to Yes), Nuclear sclerosis (No to Yes), Cortical cataract (No to Yes), and Posterior subcapsular cataract (No to Yes)
 - iv. Summary table of number of subjects (%) underwent surgery due to cataract post-baseline.
- m. FUNDUS Photograph: Shift table from baseline to worst post-baseline by eye (R/L) and subject (worse eye) for Vitreous normal in appearance (Yes to No), PVD (No to Yes), Vitreous cell (No to Yes), Vitreous haze (No to Yes), Optic nerve normal in appearance (Yes to No), and Retina normal in appearance (Yes to No).
2. General study from EOT visit to last follow-up visit: To assess the change in corneal findings after discontinuation of study treatment, among eyes and subjects (worse eye) with exam finding at EOT visit worse than baseline, the following analyses will be performed.
- a. Summary of change (worsening, no change, improvement) from EOT to last follow-up visit based on categories defined below by eye (R/L) and subject (worse eye)
 - b. Summary of number (%) of eyes and subjects (worse eye) that resolve (improve to baseline level or better based on categories defined below), and descriptive summary of time from EOT visit to resolution among eyes and subjects (worse eye) that resolved

The parameters included in above analyses are:

1. BCVA change from baseline in log MAR scale (< 0.12 , ≥ 0.12 to < 0.3 , ≥ 0.3)
 2. IOP (≥ 22 mm Hg/ <22 mm Hg)
 3. Corneal epithelium (Normal/Abnormal), Punctate Keratopathy (None/Mild /Moderate/Severe), Corneal ulcer (No/Yes), Microcystic edema (No/Yes), Microcystic without edema (No/Yes), Subepithelial haze (No to Yes), Corneal neovascularization (No to Yes), Stroma (Normal/Abnormal); Active opacity (No/Yes); Active edema (No/Yes)
 4. Corneal endothelium (Normal/Abnormal), Descemet's folds (No/Yes; Peripheral/Central), Endothelial lesion (Peripheral/Central)
 5. Pachymetry (increase from baseline $< 5\%$, and $\geq 5\%$), Tear break up time (≤ 5 mm, > 5 and ≤ 10 mm, and > 10 mm), Schirmer's test (≤ 5 sec, > 5 and ≤ 10 sec, and > 10 sec)
3. Ocular sub-study (Cycle 1-4): To evaluate the effect of topical corticosteroids on corneal findings, pending on the availability of data, the following analyses will be performed in up to 30 participants who will receive monocular topical corticosteroids for the first 4 cycles:
- a. Summary of worst grade during Cycle 1-4 of corneal events (GSK scale) in eyes randomized to topical corticosteroids treatment and eyes not.
 - b. BCVA at baseline, at worst during Cycle 1-4, and worst and most frequent category (definite worsen, possible worsen, and no change/improved) of change from baseline during Cycle 1-4 will be summarized in eyes randomized to topical corticosteroids treatment and eyes not. Eyes with a decline in BCVA to 'light perception' (LP) or 'no light perception' (NLP) due to corneal finding anytime post-baseline will also be summarized.
 - c. Summary of onset time to first study treatment (BCMA)-related corneal finding (GSK scale) in eyes randomized to topical corticosteroids treatment and eyes not.
 - d. Summary of onset time to initiation of topical corticosteroids treatment in eyes randomized to no such treatment.
 - e. Shift in corneal findings (per ocular exam) from baseline to worst during Cycle 1- 4 in eyes randomized to topical corticosteroids treatment and eye not. Corneal findings include Corneal epithelium (Normal to Abnormal), Punctate Keratopathy (None/Mild to Moderate/Severe), Corneal ulcer (No to Yes), Microcystic edema (No to Yes), Microcystic without edema (Yes to No), Subepithelial haze (No to Yes), Corneal neovascularization (No to Yes), Stroma (Normal to Abnormal), Active opacity (No to Yes), and Active edema (No to Yes).

The details of the planned displays are provided in [Appendix 13](#): List of Data Displays.

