3.0360	Full Safety	ESI2b	Summary of Onset and Duration of the First Occurrence of Corneal Events (GSK Scale) of Grade 3 or Above	Algorithm of duration calculation need to be updated to follow what was done in T3.1171 in 117159 (Primary_02).	SAC [1] , SAC [2]
3.0910	Full Safety	ESI2b	Summary of Onset and Duration of the First Occurrence of Corneal Events (GSK Scale) of Grade 2 or Above	Algorithm of duration calculation need to be updated to follow what was done in T3.1171 in 117159 (Primary_02).	Headline, SAC [1] ,SAC [2]
3.0911	Full Safety	Mock-up SAFE_T21	Summary of Characteristics II of Corneal Events (GSK Scale) of Grade 2 or Above		SAC [1] ,SAC [2]
3.0912	Full Safety	Mock-up SAFE_T21	Summary of Characteristics II of Visual Acuity (GSK Scale) of Grade 2 or Above		SAC [1] ,SAC [2]
3.0370	Full Safety	Mock-up SAFE_T2a	Summary of Corneal Events (GSK Scale) Leading to Action Taken with Study Treatment		SAC [1] , SAC [2]
3.0380	Full Safety	Mock-up SAFE_T2	Summary of Action Taken with Study Treatment for Corneal Events (GSK Scale) by Visit	No need to include EOT visit. Add footnote that Visits 'Cycle 1-4 Day 1/Day 10' are from ocular sub-study subjects only.	SAC [1] , SAC [2]
3.0410	Full Safety	Mock-up SAFE_T3	Shift in Grade of Corneal Events (GSK Scale) from EOT to Last Follow-Up		SAC [1] , SAC [2]
3.0420	Full Safety	Mock-up SAFE_T4a	Summary of resolution in Grade of Corneal Events (GSK Scale) from EOT to last Follow-Up.		SAC [1] , SAC [2]
3.0430	Full Safety	Mock-up SAFE_T4b	Summary of Time to Re-initiation of Study Treatment Post Treatment Delay due to Corneal Events (GSK Scale)		SAC [1] , SAC [2]
3.0440	Evaluable	Programming note	Summary of Worst Post-Baseline Corneal Findings (GSK Scale) Evaluable	This table was already produced by Veramed at IA	IA [1]

CONFIDENTIAL

205678

Safety: Tables					
No.	Population	IDSL / Example Shell	Title	Programming Notes	Deliverable [Priority]
3.0441	Full Safety	Programming note	Summary of Worst Post-Baseline Corneal Events (GSK Scale)	Could also use T3.0440 produced by Veramed at IA as template.	SAC [1]
3.0920	Full Safety	Programming note	Summary of Worst Post-Baseline Corneal Events (GSK Scale) by Best Response Based on Independent Review Committee	Best Response categories: (PR/VGPR/CR/sCR vs. otherwise). Could also use T3.0440 produced by Veramed at IA as template.	SAC [1] ,SAC [2]

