3.0810	Full Safety	Mock-up SAFE_T9	Shift in Blepharitis/MGD from Baseline to Worst Post-Baseline	By eye (R/L) and subject (worse eye). See Section 8.5 Ocular findings from ophthalmic exam for details.	SAC [1]
3.0820	Full Safety	Mock-up SAFE_T9	Shift in Conjunctival Exam Findings from Baseline to Worst Post-Baseline	By eye (R/L) and subject (worse eye). Create shift table for each of 3 findings: Chemosis (Absent/Present); Bulbar Conjunctiva White and Quiet: (Yes/No); Palpebral Conjunctiva within normal limits (Yes/No); See Section 8.5 Ocular findings from ophthalmic exam for details.	SAC [1]
3.0840	Full Safety	Mock-up SAFE_T9	Shift in Scleritis from Baseline to Worst Post-Baseline	By eye (R/L) and subject (both eyes in same ocular exam). See Section 8.5 Ocular findings from ophthalmic exam for details.	SAC [1]
3.0852	Full Safety	Mock-up SAFE_T9	Shift in Corneal Epithelium Findings from Baseline to Worst Post-Baseline	By eye (R/L) and subject (worse eye). See Section 8.5 Ocular findings from ophthalmic exam for details.	SAC [1] ,SAC [2]

CONFIDENTIAL

205678

Safety: Tables					
No.	Population	IDSL / Example Shell	Title	Programming Notes	Deliverable [Priority]
3.0851	Full Safety	Mock-up SAFE_T9	Shift in Corneal Epithelium Findings from Baseline to Worst Post-Baseline for Microcysts without Edema		SAC [1],SAC [2]
3.0850	Full Safety	Mock-up SAFE_T9	Shift in Corneal Epithelium Findings from Baseline to Worst Post-Baseline for Corneal Epithelium and Corneal Stroma		SAC [1],SAC [2]
3.0860	Full Safety	Mock-up SAFE_T14	Summary of Findings for Punctate Keratopathy	By eye (R/L) and subject (worse eye). See Section 8.5 Ocular findings from ophthalmic exam for details.	SAC [1],SAC [2]
3.0930	Full Safety	Mock-up SAFE_T9	Shift in Corneal Endothelium Findings from Baseline to Worst Post-Baseline	By eye (R/L) and subject (worse eye). See Section 8.5 Ocular findings from ophthalmic exam for details.	SAC [1]
3.0940	Full Safety	Mock-up SAFE_T12	Summary of Presence of Descemet's Folds/ Endothelial Lesion at Any Time Post-Baseline	By eye (R/L) and subject (either eye). See Section 8.5 Ocular findings from ophthalmic exam for details.	SAC [1]
3.0970	Safety	Mock-up SAFE_T10	Summary for Change from Baseline in Pachymetry	See Section 8.5 Ocular findings from ophthalmic exam for details. Pachymetry: decrease in value means improvement;	SAC [1]

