		Grade 3	xx (xx%)	xx (xx%)	xx (xx%)
		Grade 4	xx (xx%)	xx (xx%)	xx (xx%)
	xx	All Grade	xx (xx%)	xx (xx%)	xx (xx%)
		Grade 1	xx (xx%)	xx (xx%)	xx (xx%)
		Grade 2	xx (xx%)	xx (xx%)	xx (xx%)
		Grade 3	xx (xx%)	xx (xx%)	xx (xx%)
		Grade 4	xx (xx%)	xx (xx%)	xx (xx%)

Week 7

.....

Treatment Group B (N=xx)

.....

Note: n reflects the number of participants with available GSK scale data at a given visit.
Visits 'Cycle 1-4 Day 1/10' are from ocular sub-study subjects only.

Example SAFE_T2a
 Protocol: 205678
 Population: Safety

Table X.X
 Summary of Corneal Events (GSK Scale) Leading to Action Taken with Study Treatment

Action Taken with Study treatment	Grade	Treatment	Treatment
		Group A (N = xx)	Group B (N = xx)
Study treatment withdrawn	All Grades	xx (xx%)	xx (xx%)
	Grade 1	xx (xx%)	xx (xx%)
	Grade 2	xx (xx%)	xx (xx%)
	Grade 3	xx (xx%)	xx (xx%)
	Grade 4	xx (xx%)	xx (xx%)
Dose reduction	All Grades	xx (xx%)	xx (xx%)
	Grade 1	xx (xx%)	xx (xx%)
	Grade 2	xx (xx%)	xx (xx%)
	Grade 3	xx (xx%)	xx (xx%)
	Grade 4	xx (xx%)	xx (xx%)
Dose interrupted/ delayed	All Grades	xx (xx%)	xx (xx%)
	Grade 1	xx (xx%)	xx (xx%)
	Grade 2	xx (xx%)	xx (xx%)
	Grade 3	xx (xx%)	xx (xx%)
	Grade 4	xx (xx%)	xx (xx%)

Note: If a given participant had multiple incidence of same action taken with study treatment, only the action with highest grade will be included in the summary.

Example SAFE_T3
 Protocol: 205678
 Population: Safety

Page 1 of 1
 (Data as of: 24APR2018)

Table X
 Shift in Grade of Corneal Events from Baseline to Worst Post-Baseline up to EOT visit

Treatment Group	Baseline		Worst post-baseline value					Missing
	n (%)	Grade 0 n (%)	Grade 1 n (%)	Grade 2 n (%)	Grade 3 n (%)	Grade 4 n (%)		
Treatment Group A (N=xx)	Grade 0	xx (xx.x)	xx (xx.x)	xx (xx.x)	xx (xx.x)	xx (xx.x)	xx (xx.x)	xx (xx.x)
	Grade 1	xx (xx.x)	xx (xx.x)	xx (xx.x)	xx (xx.x)	xx (xx.x)	xx (xx.x)	xx (xx.x)
	Grade 2	xx (xx.x)	xx (xx.x)	xx (xx.x)	xx (xx.x)	xx (xx.x)	xx (xx.x)	xx (xx.x)
	Grade 3	xx (xx.x)	xx (xx.x)	xx (xx.x)	xx (xx.x)	xx (xx.x)	xx (xx.x)	xx (xx.x)
	Grade 4	xx (xx.x)	xx (xx.x)	xx (xx.x)	xx (xx.x)	xx (xx.x)	xx (xx.x)	xx (xx.x)
	Missing	xx (xx.x)	xx (xx.x)	xx (xx.x)	xx (xx.x)	xx (xx.x)	xx (xx.x)	xx (xx.x)
	Total	xx (xx.x)	xx (xx.x)	xx (xx.x)	xx (xx.x)	xx (xx.x)	xx (xx.x)	xx (xx.x)
Treatment Group B (N=xx)							

- Baseline percentage is based on N. percentage for last post-Baseline value is based on Baseline n.

Example SAFE_T4
 Protocol: 205678
 Population: Safety

Page 1 of 1
 (Data as of: 24APR2018)

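### SAP section 8.5 counts raised IOP and certain endothelial and iris sub-findings without regard to baseline, and shell SAFE_T3 does not match the only table that cites it

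*SAP*

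**What the plan says.** **IOP.** SAP section 8.5 item 1b asks for an "Intraocular Pressure (IOP): summary table of 1) Number (%) of subjects with IOP" of 22 mm Hg or more at any post-baseline time, and for the "Number (%) of subjects who start treatment for IOP after 1st dose of study drug". These become Tables 3.0760 (shell SAFE_T8) and 3.0770 (shell SAFE_T8a).

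**Endothelial sub-findings.** Item 1i asks for a "Summary table by eye (R/L) and subject (either eye) for presence of Descemet's folds and Endothelial lesion at any post-baseline ocular exam". This is Table 3.0940, shell SAFE_T12. The same item also plans a shift table for endothelium as a whole, listed as "Shift in Corneal Endothelium Findings from Baseline to Worst Post-Baseline" (Table 3.0930).

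**Iris sub-findings.** Item 1l asks for "Summary tables of presence of iris findings", namely transillumination defect, nodules or neovascularization at any post-baseline exam (Table 3.1010, SAFE_T12). Overall iris status is in the slit-lamp shift table (3.1000).

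**GSK-scale corneal grade.** Shell SAFE_T3 in Appendix 14 is titled "Shift in Grade of Corneal Events from Baseline to Worst Post-Baseline up to EOT visit". The only display in Appendix 13 that cites it is Table 3.0410, titled "Shift in Grade of Corneal Events (GSK Scale) from EOT to Last Follow-Up".

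**The concern.** Most of section 8.5 item 1 relates the post-baseline finding to the same eye or participant at baseline, through shift tables or change from baseline. The IOP count and the named endothelial and iris sub-findings do not, and no reason is given. A participant who enters the study with the finding and keeps it is tallied exactly like one who develops it on treatment.

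Ocular findings on ophthalmic exam are part of the secondary safety endpoint (section 2.2). IOP is also of particular interest here, because the SAP summarises steroid eye-drop exposure (section 6.6) and includes a sub-study of topical corticosteroids. A reader will want to know how many elevations are new, and Table 3.0760 cannot say.

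The SAFE_T3 mismatch is a separate problem. A programmer who follows the shell would produce baseline rows and worst-post-baseline columns under a title that promises EOT to last follow-up.

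**Working it through.** No sample size, power or event count in the SAP bears on this point, so there is no figure to reproduce. The check sets the displays side by side and then illustrates the possible size.

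**1. Does any planned display separate new from pre-existing findings?**

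| Finding | Any-time count | Baseline used in it? | Baseline-to-worst shift elsewhere? |
|---|---|---|---|
| IOP 22 mm Hg or more | 3.0760, SAFE_T8 | No | None |
| Descemet's folds, endothelial lesions | 3.0940, SAFE_T12 | No | Overall endothelium only (3.0930) |
| Transillumination defect, nodules, neovascularization | 3.1010, SAFE_T12 | No | Overall iris status only (3.1000) |

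For comparison, pachymetry is reported as change from baseline (SAFE_T10), and the punctate keratopathy shell (SAFE_T14) is limited to eyes that worsened from baseline.

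**2. Do the other IOP displays fill the gap?** Table 3.0770 counts treatment starts, not pressure. Tables 3.1070 and 3.1120 cover only eyes or subjects whose IOP category at EOT is worse than at baseline. Take two participants: one at or above the threshold from entry to EOT, and one who first crosses it on treatment and is back below it by EOT. Both are counted in 3.0760 and neither enters 3.1070. The tables cannot distinguish them.

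**3. Is the baseline-to-worst GSK-scale shift scheduled anywhere?**
- Section 8.2.3 item 5 and Table 3.0410 cover EOT to last follow-up.
- Item 6 and Table 3.0441 give the worst post-baseline grade.
- Table 3.0340 (SAFE_T1) shows the baseline grade distribution, but only as a margin, not crossed with the later grade.
- SAFE_T3 has the right rows and columns for a baseline-to-worst shift, but no table with that title cites it. Its footnote also refers to the last post-baseline value, while its column header says worst.

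So no subject-level baseline-to-worst shift in GSK grade is listed for the general study. The shells do allow for non-zero baseline grades: SAFE_T1, SAFE_T3 and SAFE_T16 all carry baseline grades 1 to 4.

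**4. Illustration of size.** Let b be the share with a persisting finding at baseline and i the new incidence among those without it. The SAP gives neither, so both are assumed.

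Any-time rate = b + (1 − b) × i, with i = 5%:
- b = 0: 5.0%, the same as the new-onset rate.
- b = 3%: 0.03 + 0.97 × 0.05 = 0.0785, about 7.9%.
- b = 5%: 0.05 + 0.95 × 0.05 = 0.0975, about 9.8%.
- b = 10%: 0.10 + 0.90 × 0.05 = 0.145, or 14.5%.

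The share of the any-time count already present at baseline is b divided by that rate: 0.03/0.0785 = 38%, 0.05/0.0975 = 51% and 0.10/0.145 = 69%.

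**The case against.** The strongest reply is that section 8.5 is largely conditioned on baseline already, and that these are supplementary descriptive counts.

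- Overall endothelium and iris status have shift tables, as do the corneal epithelium findings (3.0850 to 3.0852).
- The EOT-to-follow-up analyses condition on worsening from baseline for IOP, folds and endothelial lesions.
- GSK-scale resolution (SAFE_T4a) counts only those whose grade at EOT is worse than at baseline, and baseline keratopathy is a candidate covariate in the section 8.2.3 logistic model.
- Appendix 14 holds example shells that are reused across displays, and section 8.2.3 item 5 makes the purpose of Table 3.0410 clear despite the SAFE_T3 headers.

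Much of this stands. It confines the endothelial and iris point to the named sub-findings and makes SAFE_T3 a matter of reconciling shell and table. It does not supply the missing IOP shift. The EOT analyses miss elevations that resolve before EOT, and they do not include the iris sub-findings at all.

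A reader might infer that rates of the drug's main ocular toxicity are overstated because pre-existing findings are counted as treatment effects. The SAP does not support that. It does not label these counts treatment-emergent or drug-related, and it analyses eye disorder adverse events separately. The GSK-scale grading rules are left to the protocol, and the template for Table 3.0441 is not shown, so whether baseline enters either cannot be judged. The SAFE_T3 mismatch also causes none of the IOP, endothelial or iris counts.

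**Conclusion.** The point holds in limited form. Table 3.0760 cannot separate new from pre-existing raised IOP, and no other display does so. Tables 3.0940 and 3.1010 share the gap for their sub-findings only. Independently, SAFE_T3 and Table 3.0410 contradict each other, and no subject-level baseline-to-worst shift in GSK grade is scheduled.

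The effect on the reported percentages is unknown. The illustrative 7.9-14.5% against 5% rests wholly on assumed prevalence, assumed incidence and full persistence of baseline findings; with zero baseline prevalence there is no difference. The primary analysis of ORR is not affected. The case for acting is that the tables would then answer the question a safety reader asks, by the method the section already uses for most other findings.

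**What to change.** 1. Keep the any-time counts in 3.0760, 3.0940 and 3.1010. Add to each either a baseline-to-worst shift or a new-onset row, with eyes or subjects free of the finding at baseline as the denominator (for IOP, below the SAP's own 22 mm Hg cut). State how missing baseline exams are handled.
2. Give Table 3.0410 a shell with EOT grade in the rows and last-follow-up grade in the columns.
3. Attach SAFE_T3 to its own table of GSK-scale grade from baseline to worst post-baseline, and make its footnote and column header agree.

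The cost is shell and programming-note edits, one new table and the related reruns. Section 8.5 says that ophthalmic exams are already scheduled at screening, so no new data are needed. Appendix 13 lists 3.0760 and 3.0940 for the primary analysis only, and 3.1010 and 3.0410 for the end-of-study analysis as well. The first two would therefore have to be added to the end-of-study deliverable for the change to appear there.

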3.0980	Full Safety	Mock-up SAFE_T7	Summary for Change from Baseline to Worst Post-Baseline in Schirmer's Test and Tear Break-up Time	See Section 8.5 Ocular findings from ophthalmic exam for details. Tear break-up time/Schirmer's test: increase in value means improvement.,	SAC [1] ,SAC [2]
3.1340	Full Safety	Mock-up SAFE_T9a	Shift in Schirmer's Test from Baseline to Worst Post-Baseline	See Section 8.5 Ocular findings from ophthalmic exam for details	SAC [1]
3.1350	Full Safety	Mock-up SAFE_T9a	Shift in Tear Break-up Time from Baseline to Worst Post-Baseline	See Section 8.5 Ocular findings from ophthalmic exam for details	SAC [1]
3.1000	Full Safety	Mock-up SAFE_T9	Shift in Slit Lamp Exam Findings from Baseline to Worst Post-Baseline	By eye (R/L) and subject (worse eye). See Section 8.5 Ocular findings from ophthalmic exam for details.	SAC [1] ,SAC [2]

Safety: Tables					
No.	Population	IDSL / Example Shell	Title	Programming Notes	Deliverable [Priority]
3.1010	Full Safety	Mock-up SAFE_T12	Summary of Presence of Iris Findings at Any Time Post-Baseline	By eye (R/L) and subject (either eye). Summary tables for number (%) of eyes with 'Transillumination defect', 'Nodules', or 'Neovascularization' at any post-baseline ocular exam. See Section 8.5 Ocular findings from ophthalmic exam for details.	SAC [1] ,SAC [2]
3.1020	Full Safety	Mock-up SAFE_T9	Shift in Pseudophakia and Cataracts from Baseline to Worst Post-Baseline	By eye (R/L) and subject (worse eye). See Section 8.5 Ocular findings from ophthalmic exam for details.	SAC [1]
3.1040	Full Safety	Mock-up SAFE_T8	Number of Subjects (%) Underwent Surgery due to Cataract Post-Baseline		SAC [1]
3.1050	Full Safety	Mock-up SAFE_T9	Shift in Findings from FUNDUS Photograph from Baseline to Worst Post-Baseline	By eye (R/L) and subject (worse eye). See Section 8.5 Ocular findings from ophthalmic exam for details.	SAC [1]
Ocular findings for General study from EOT to last follow-up visit					
3.1060	Full Safety	Mock-up SAFE_T15	Summary of Change (Worsening, No Change, Improvement) in Best Corrected Visual Acuity (BCVA) from EOT Visit to Last Follow-Up Visit	By eye (R/L) and subject (worse eye).	SAC [1] ,SAC [2]
3.1070	Full Safety	Mock-up SAFE_T15	Summary of Change (Worsening, No Change, Improvement) in Intraocular Pressure (IOP) from EOT Visit to Last Follow-Up Visit	By eye (R/L) and subject (worse eye). For IOP, decrease in value means improvement.	SAC [1]

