	No Change	330 (96%)	359 (98%)
	Improvement	11 (3%)	4 (1%)
Left eye	n	342	364
	Worsening	1 (<1%)	2 (<1%)
	No Change	330 (96%)	359 (98%)
	Improvement	11 (3%)	4 (1%)
Subject (Worse eye)	n	342	364
	Worsening	1 (<1%)	2 (<1%)
	No Change	330 (96%)	359 (98%)
	Improvement	11 (3%)	4 (1%)

n is the number of eyes or subjects (worse eye) with exam findings at EOT visit worse than baseline, which will be used as denominator to calculate the percentage.

Example SAFE_T16
 Protocol: 205678
 Population: Safety

Table x.xxxx

Summary of Worst Grade of Corneal Events (GSK Scale) during Cycle 1-4 by Randomized Topical Corticosteroids Treatment

Timepoint		Treatment Group A (N = xx)		Treatment Group B (N = xx)	
		Eyes randomized to corticosteroids	Eye randomized to no corticosteroids	Eyes randomized to corticosteroids	Eyes not randomized to corticosteroids
Baseline	n	100	100	100	100
	Grade 0	70 (70%)	70 (70%)	70 (70%)	70 (70%)
	Grade 1	20 (20%)	20 (20%)	20 (20%)	20 (20%)
	Grade 2	10 (10%)	10 (10%)	10 (10%)	10 (10%)
	Grade 3	0	0	0	0
	Grade 4	0	0	0	0
Worst during Cycle 1-4	n	100	100	100	100
	Grade 0	70 (70%)	70 (70%)	70 (70%)	70 (70%)
	Grade 1	20 (20%)	20 (20%)	20 (20%)	20 (20%)
	Grade 2	10 (10%)	10 (10%)	10 (10%)	10 (10%)
	Grade 3	0	0	0	0
	Grade 4	0	0	0	0

Example SAFE_T17
 Protocol: 205678
 Population: Safety

Table x.xxxx
 Summary of Best Corrected Visual Acuity(BCVA) score (logMAR score) during Cycle 1-4 by Randomized Topical
 Corticosteroids Treatment

Timepoint	BCVA Score	Treatment Group A (N =xx)		Treatment Group B (N =xx)	
		Eyes	Eye not to	Eyes Randomized to	Eyes not to
Baseline	N	xxx	xxx	xxx	xxx
	Mean	x.x	x.x	x.x	x.x
	SD	x.xx	x.xx	x.xx	x.xx
	Median	x.x	x.x	x.x	x.x
	Min	x	x	x	x
	Max	xxx	xxx	xxx	xxx
Worst during Cycle 1-4	n	xxx	xxx	xxx	xxx
	Mean	x.x	x.x	x.x	x.x
	SD	x.xx	x.xx	x.xx	x.xx
	Median	x.x	x.x	x.x	x.x
	Min	x	x	x	x
	Max	xxx	xxx	xxx	xxx
	n	xxx	xxx	xxx	xxx
Worst change from baseline during Cycle 1-	No change/improve	xx(x.x%)	xx(x.x%)	xx(x.x%)	xx(x.x%)
	Possible worsened	xx(x.x%)	xx(x.x%)	xx(x.x%)	xx(x.x%)
	Definite worsened	xx(x.x%)	xx(x.x%)	xx(x.x%)	xx(x.x%)
Most frequent change from baseline during cycle 1-4	No change/improve	xx(x.x%)	xx(x.x%)	xx(x.x%)	xx(x.x%)
	Possible worsened	xx(x.x%)	xx(x.x%)	xx(x.x%)	xx(x.x%)
	Definite worsened	xx(x.x%)	xx(x.x%)	xx(x.x%)	xx(x.x%)
Worst during Cycle 1-4	BCVA decline to light perception	xx(x.x%)	xx(x.x%)	xx(x.x%)	xx(x.x%)
	BCVA decline to no light perception	xx(x.x%)	xx(x.x%)	xx(x.x%)	xx(x.x%)

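### In the EOT-to-last-follow-up eye-exam change tables, worsening is impossible by construction for ten two-level findings, and new onset after EOT is not shown separately

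*SAP*

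**What the plan says.** The aim of Section 8.5 item 2 is stated broadly: "To assess the change in corneal findings after discontinuation of study treatment". The same sentence restricts both analyses that follow: "among eyes and subjects (worse eye) with exam finding at EOT visit worse than baseline, the following analyses will be performed".

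Item 2a is the change summary: "Summary of change (worsening, no change, improvement) from EOT to last follow-up visit based on categories defined below by eye (R/L) and subject (worse eye"). Item 2b summarises resolution to baseline level or better, and the time to it, in the same restricted set.

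The listed categories are mostly two-level, for example "Active opacity (No/Yes); Active edema (No/Yes"). Some scales are longer, for example "Punctate Keratopathy (None/Mild /Moderate/Severe").

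Appendix 13 assigns shell SAFE_T15 to Tables 3.1060 to 3.1100. Its footnote repeats the restriction as the denominator: "n is the number of eyes or subjects (worse eye) with exam findings at EOT visit worse than baseline". The shell nevertheless prints a Worsening row for right eye, left eye and worse eye. Table 3.1070, titled "Summary of Change (Worsening, No Change, Improvement) in Intraocular Pressure (IOP) from EOT Visit to Last Follow-Up Visit", carries a programming note that describes improvement as a fall in the value, not as a move between categories.

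**The concern.** The inclusion rule and the outcome classes in item 2a do not fit together. The rule admits only eyes that have already deteriorated on the finding, while the table offers deterioration as one of three outcomes. On a two-level finding, the eyes that could still worsen are those at the better level at EOT, and the rule removes them.

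Ocular findings on ophthalmic exam are a safety endpoint in Section 2.2, and eye disorder and corneal events are adverse events of special interest in Section 8.2. A zero in the Worsening row could be read as evidence that findings only stabilise or improve after discontinuation, when the zero comes from the denominator.

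**Working it through.** The SAP gives no figure to reproduce here, so the check is a count of parameters and of logically possible paths. Path counts are not rates.

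**Parameters listed under Section 8.5 item 2**
- BCVA change: three levels.
- IOP: two levels, cut from a continuous value.
- Corneal epithelium, ulcer, microcystic edema, microcystic without edema, subepithelial haze, neovascularization, stroma, active opacity, active edema: two levels each (nine).
- Punctate keratopathy: four levels.
- Corneal endothelium: two levels.
- Descemet's folds: absent, or present as peripheral or central.
- Endothelial lesion: peripheral or central, with no absent level or order given, so it is not classified here.
- Pachymetry: two levels, cut from a continuous value.
- Tear break-up time and Schirmer's test: three levels each.

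Total: 1 + 1 + 9 + 1 + 1 + 1 + 1 + 1 + 2 = 18. Purely two-level: 9 + 1 = 10. Two-level after cutting a continuous value: 2.

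**Paths.** Take k ordered levels, higher being worse, at baseline (b), EOT (e) and last follow-up (f). Eligible means e > b; worsening means f > e.
- All paths: k³
- Eligible paths: k × C(k,2)
- Worsening paths without the restriction: k × C(k,2)
- Worsening paths kept by the restriction (b < e < f): C(k,3)

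| k | all | eligible | worsening, unrestricted | kept | excluded |
|---|---|---|---|---|---|
| 2 | 8 | 2 | 2 | 0 | 2 |
| 3 | 27 | 9 | 9 | 1 | 8 |
| 4 | 64 | 24 | 24 | 4 | 20 |

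For k = 2 the eligible paths are No/Yes/Yes (no change) and No/Yes/No (improvement). The excluded worsening paths are No/No/Yes, which is new damage after EOT, and Yes/No/Yes, which is recurrence.

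BCVA is categorised by change from baseline, so its baseline is always in the lowest category. By category there are then three worsening moves (low to middle, low to high, middle to high). Only the last is kept, so 2 of 3 are excluded.

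**IOP by category or by value.** Take an illustrative path of 15, 18, 23 mm Hg. By category (cut at 22) the eye is below the cut at baseline and at EOT, so it is not eligible. By value, 18 > 15 makes it eligible, and moving from 18 to 23 crosses the cut and counts as worsening. The lead-in does not say which rule applies.

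**Illustration (assumed counts).** Suppose 100 eyes are clear at baseline; at EOT 10 have the finding and 90 do not, and 9 of the 90 develop it later. The planned table shows worsening 0/10; the full set shows 9/100 = 9%. If the number of new cases ranges from 0 to 90, the full set ranges from 0% to 90%, while the planned row stays at 0/10.

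**The case against.** The best defence is that item 2 asks a reversibility question: what becomes of damage present when treatment stops. The restriction stands in the same sentence as the aim, and the SAFE_T15 footnote discloses it. That holds for item 2b. It does not explain why item 2a offers a worsening class that ten findings cannot enter.

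Three stronger readings are tempting, and the SAP does not support them.

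- A reader might infer that damage first appearing after EOT is not counted at all. Section 8.5 item 1 runs from baseline to last follow-up. Its shift tables take the worst post-baseline value with no EOT condition, IOP of 22 mm Hg or more is counted at any time post-baseline, and BCVA is summarised at EOT and at last follow-up. On the GSK scale, Table 3.0410 is titled as a shift from EOT to last follow-up. Tables 3.0911 and 3.0912 (shell SAFE_T21) include onset after treatment exposure. Such damage is therefore counted, but item 1 mixes it with on-treatment damage and SAFE_T21 pools it with events unresolved at end of exposure.
- A reader might infer that Tables 3.1070 to 3.1100 must show no worsening. Table 3.1080 includes punctate keratopathy, Table 3.1090 Descemet's folds, and Table 3.1100 tear break-up time and Schirmer's test; these can show some. Table 3.1070 depends on the unstated IOP rule.
- A reader might infer that no planned display separates new onset after EOT. Tables 3.12771 and 3.12781 (corneal exam finding and BCVA characteristics) point to earlier outputs that are not in the SAP, so this cannot be checked. The claim must be limited to summaries whose layout the SAP gives.

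**Conclusion.** The point holds in limited form. For ten of 18 parameters the Worsening row in item 2a is 0 by construction; for IOP and pachymetry this is so only if eligibility is by category. For ordered scales with three or four levels most worsening paths are excluded (8 of 9, or 20 of 24; 2 of 3 for BCVA). No exam-level summary with a layout in the SAP isolates damage first appearing after EOT.

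This assumes that eligibility is applied finding by finding, which is the natural reading of SAFE_T15. It also assumes that Descemet's folds, if treated as a multi-level scale, are ordered absent, peripheral, central; the SAP does not say so. The tables are descriptive and no hypothesis test is affected, but they bear on a stated safety endpoint and the correction is cheap.

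**What to change.** 1. Keep the restriction to eyes and subjects worse than baseline at EOT for item 2b and its resolution tables (3.1110 to 3.1150, shell SAFE_T4).
2. For item 2a and SAFE_T15 (Tables 3.1060 to 3.1100), tabulate EOT against last follow-up for all eyes and subjects with an EOT exam and a later follow-up exam. Give new onset after EOT its own row.
3. Keep the restricted count visible beside it. The share improved will fall because unaffected eyes enter the denominator: in the illustration above, even if all 10 affected eyes improved, 10/10 would become 10/100.
4. State whether worse than baseline is judged by category or by value, at least for IOP, pachymetry and the other measured quantities.
5. Align the shell assigned to Table 3.0410. SAFE_T3 is laid out as baseline to worst post-baseline up to EOT, while the table title is EOT to last follow-up.

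The cost is SAP wording, a denominator change in five tables and one shell correction, with no new data. Tables 3.1060, 3.1080 and 3.1090 are already due again at end of study. Tables 3.1070 and 3.1100 are listed for the primary analysis only and would have to be added to the end-of-study package.
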